#### **6.1 Informed Consent**

No study activities will be conducted until an IRB approval is obtained. Potential participants who may be eligible will be approached by the research staff. The research staff will only introduce the study with the patients after a member of the clinical care team acquires permission from the potential participant that they can be approached for a study. If interested, the research staff will discuss the study and obtain an informed consent from the participant.

Sufficient time will be given to participants to read the consent form, and to ask questions to ensure understanding.

An IRB-approved study brochure may be given to potential participants to provide more information about the study and the procedures involved.

# **6.2 Randomization visit: Study Groups**

There will be 2 intervention groups, active treatment or standard care, based on randomization.

# Group 1 (active treatment):

The starting dose and escalation of therapy in the active treatment arm are as follows:

Ferumoxytol: The patient will receive infusions at the Stanford's CTRU or in the Antepartum Unit

Ferumoxytol will be administered to participants with iron deficiency anemia with inclusion criteria as outlined above. Each single use vial contains 510 mg elemental iron / 15 mL.

Prior to infusion of ferumoxytol, patients will receive 650mg of Tylenol.

Participants with Hemoglobin between 9-10.9 g/dL will receive one dose of ferumoxytol (510mg). Participants with Hemoglobin between 7-8.9 g/dL will receive two doses (total 1020mg) of ferumoxytol with 3-8 days interval between doses per manufacturer instructions. The IV iron is administered as an infusion for approximately 15 – 30 minutes. Patients will receive the IV iron at Stanford's Clinical and Translational Research Unit (CTRU) outpatient clinics under the administration under trained Advanced Practitioner Provider/Research Clinic Nurse coordinator or in the inpatient Antepartum Unit. When administered via infusion, administer diluted as a slow IV infusion over at least 15 minutes. Patient should be in a reclined or semi-reclined position during the infusion; monitor for signs of hypersensitivity (including blood pressure and pulse) for at least 30 minutes after infusion. In the case hypersensitivity or side effects to medication, patients will be treated according to standard clinical guidelines, which may include administering Benadryl, Zofran, steroids, albuterol nebulizer, and in the cases of serious hypersensitivity, intramuscular epinephrine.

**Note:** Serious hypersensitivity reactions have been observed with rapid IV injection (<1 minute) (Macdougall 2014; Vadhan-Raj 2014). Wait ≥30 minutes between administration of ferumoxytol and other agents that may cause serious hypersensitivity reactions and/or hypotension (e.g., chemotherapy, monoclonal antibodies).

# Group 2 (standard of care):

Ferrous sulfate: the patient will receive a bottle dispensed with 100 pills at a time.

Oral ferrous sulfate will be administered to participants identified with iron deficiency anemia as described above. One tablet every other day in patients with hemoglobin 9-10.9 g/dL and two tablets every other day will be provided for patients with hemoglobin levels between 7- 8.9 g/dL.

[figure not shown]
Tablet: 325 mg [elemental iron 65 mg].

# 6.3. Starting dose of Medications

Historically, suggested dosing of oral ferrous sulfate has been increased in frequency up to 2-3 times per day for treatment of anemia. However, this practice has come into question as women often have difficulty with completing oral treatment due to gastrointestinal side effects. Immediate release oral iron products are preferred for treatment of iron deficiency anemia; enteric coated and slow/sustained release preparations are not desired due to poor absorption (Hershko 2014; Liu 2012). Moreover, hepcidin has been found to be elevated immediately after taking oral iron, transiently decreasing absorption (Moretti 2015). A recent open-label, randomized controlled trials showed higher amounts of iron absorption with dosing every other day compared two daily dosing, with subsequent studies showing similar findings (Stoffel et. al., 2017). Thus, oral iron with be dosed every other day in this study.

The dosing for intravenous iron was initially based on the Ganzoni formula. However, it was noted to be cumbersome as it was not practical to dose outside of the confines of elemental iron in the viable. Thus, in clinical practice patients have received the standard dosing 510mgx2 and recently there was an investigation by Auerbach et al which demonstrated the efficacy of single dosing of 1020mg in a single infusion (MA).

Algorithm A: Randomization

#### 7. POST RANDOMIZATION VISITS AND MANAGEMENT OF IDA

# 7.1 Post Randomization Visits and management of IDA for both groups at 4 weeks

Group 1: (IV iron) Follow up visits

Important for patient to maintain prenatal care, beyond 28 weeks gestation: frequency of visits determined by primary OB, this is often every 1-2 weeks

- 4 weeks post treatment labs to be timed with prenatal visit if possible. The CTRU is conveniently located adjacent to Stanford/LPCH OB clinic
  - if less than starting hemoglobin, then refer to hematologist

# Group 2: (oral iron)

- 4 weeks post-initiation labs to be timed with prenatal care where possible
- Pill count to occur with CTRU or MFM research staff to assess compliance
  - If compliance a concern, assess reasons why

In both groups, patient will complete a survey monitoring symptoms and adverse effects.

# 7.2 Post Randomization Visits and management of IDA for both groups at 8 weeks

Group 1: (IV iron) Follow up visits

Important for patient to maintain prenatal care, beyond 28 weeks gestation: frequency this is often every 1-2 weeks

[figure not shown]
 8 weeks post-completion treatment labs to be timed with prenatal visit if possible. The CTRU is conveniently located adjacent to Stanford/LPCH OB clinic

# Group 2: (oral iron)

- 8 weeks post-initiation labs to be timed with prenatal care where possible
- Pill count to occur with CTRU or MFM research staff to assess compliance
  - If compliance a concern, assess reasons why

[figure not shown]
In both groups, patient will complete a survey monitoring symptoms and adverse effects between 8-12 weeks after initiation of therapy.

Algorithm B: Eval for labs post 4 weeks treatment

\* Oral arm: if patients state they are intolerant to oral iron at any time during the study – refer to OB to discuss alternative treatment options

# Algorithm C: Evaluation of Labs 8 weeks post treatment

\*Oral arm: if patients state they are intolerant to oral iron at any time during the study – refer to OB to discuss alternative treatment options

# 7.3 Management of patient's intolerance to study intervention

#### Oral iron:

For adverse effects, particularly GI, consideration may be given for IV iron as this is standard of care. Per ACOG, intravenous iron is an approved indication for patient's intolerant of oral iron.

#### Intravenous iron:

For adverse effects such as hypotension (maternal BP<90/60) and persistent dizziness, headaches, lightheadedness or fatigue and no other potential cause other than the medication, will be assessed for adverse reactions and any signs of anaphylaxis. Methylprednisolone, solumedrol, or dexamethasone, albuterol nebulizers, and intramuscular epinephrine will be available on site for any immediate concerns.

PLEASE REFER TO THE DETAILED ALGORTIHM APPROACH FOR MANAGEMENT OF ADVERSE REACTIONS: this is a figure from Rampton, et a "Hypersensitivity reactions to intravenous iron: guidance for risk minimization and management."

For patients that are stable for transfer, the plan will be for obstetric monitoring and further evaluation at the LPCH OB triage on the third floor. The location is across the street from the CTRU and Stanford/LPCH clinic. The patients will still be followed by the study in intent to treat fashion. In the cases of an unstable patient, 911 will be called and patient will be transferred immediately to the emergency room.

To increase effective management of possible hypersensitivity reactions in the IV group: the following have been included.

- Reference range of normal vitals in pregnancy
- Algorithm for management of hypersensitivity reactions

[figure not shown]

Figure 1. Algorithm outlining grading and management of acute hypersensitivity reactions to intravenous iron infusions. Details are given in the text.

- I. Management of mild Hypersensitivity reactions
- II. Mild of Moderate Hypersensitivity reactions
- III. Severe/life threatening Hypersensitivity reactions

Note: Methyl prednisone prior to IV infusion may considered on case by case basis for patients with history of asthma or high risk medication allergy.

Visit Description	Screening/ Enrollment	Treatment		4 weeks	8 weeks	Delivery	1 day	6 weeks
		IV Ferumoxytol	Oral Ferrous sulfate	Post-initiation/ Post- completion	Post-initiation/ Post- completion		Postpartum	postpartum
Visit Window	24-34 weeks GA	24-34 weeks	24-34 weeks GA up to delivery	•	•		1 day after delivery	
Screening of pregnant women with eligible hemoglobin and ferritin levels	X		•					
Review eligibility criteria	X							
Informed consent	X							
Iron studies with or without baseline complete metabolic panel (depending on history of liver or kidney disease)	X							
Randomization	X							
Assign study number	X							
Demographics	X							
Medical and obstetric history review	X							
Initiate Oral iron study medications			X					
Schedule a visit at the CTRU for IV Iron infusion or coordinate with Antepartum Unit		X						
IV iron infusion appointment, 1st session		X						
Second IV iron infusion, as needed based on initial hemoglobin levels		X						
Monitoring during the IV Iron infusion and post-infusion period		X						
Blood draw to check CBC at 4 weeks after initiation of oral iron/ post-completion of IV infusions				X				
Blood draw to check CBC 8 weeks after initiation of oral iron/ post-completion of IV infusions					X			
Blood draw to check CBC during the time of admission for delivery (SOC)						X		
Blood draw to check hemoglobin, hematocrit level post-delivery (SOC)							X	(per OB)
SAE/ AE monitoring, reporting, recording		X	X	X	X	X	X	X
Pregnancy/ prenatal data collection						X		
Delivery data collection						X	X	
Neonatal data collection						X	X	

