# **Inclusion Criteria:**

- 1. Pregnant patients 18 years old and above receiving prenatal care at Stanford/LPCH OB clinic
  - a. Hemoglobin < 11 g/dL, serum ferritin < 30 ug/dL and or transferrin saturation (TSAT) < 20%
  - b. Between 24-34 weeks' pregnancy
  - c. (study will offer iron studies to determine eligibility for patients eligible by hemoglobin if labs not ordered by primary obstetrician/health care provider per standard of care)
- 2. Singleton pregnancy
- 3. Viable Pregnancy
- 4. Hemodynamically stable

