#### 3.2 Secondary Outcome

Evaluate the

- rate of patients who discontinued treatment,
- the rate of adverse events associated with treatment,
- the need for blood transfusion postpartum
- symptoms of patients before, during, and at the completion of therapy

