# 5.4 Screening/Re-screening

Patients may be included in the study up to 34 weeks 6/7 days. If the above inclusion criteria are met and exclusion criteria are absent, patients should be approached for study participation (if not already done) and randomization. All women who have a diagnosis of IDA should have the screening form initiated. The screening number will be generated electronically with REDCap is accessed and participant information is entered.

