Patients in both groups will complete post-intervention surveys at 1 week, 4 weeks, and 8-12 weeks after initiating therapy to monitor symptoms and adverse events.

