# 7.7 Participant follow up

A clinic visit (preferred method) or follow up call will occur at 6 (4-12 weeks) weeks after delivery in accordance with routine postpartum care. Several data forms will be used during this follow-up process using forms for maternal outcomes, newborn outcomes, NICU outcomes, and 6 weeks follow up forms. These forms, HIPAA compliant, will be entered into the REDCap database.

At randomization, 24-28 weeks (up to 30 complete weeks if necessary) 4 and 8 weeks post-initiation (Oral iron)/ post-treatment (IV iron) labs will be collected as described above. We will also perform chart abstraction to determine hemoglobin levels at the time of admission for delivery and 1 day postpartum (these labs are drawn routinely at LPCH).

In addition to routine prenatal and postpartum clinic visits, participants will be followed up to ascertain maternal and infant status related to re/admissions and ER or unscheduled visits. The records of any ER visits or hospitalizations will be obtained for review.

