# 7.9 Biospecimens

7.9.1 Maternal Blood Samples will be collected at the following time points (see table below):

- Randomization (at 24-28 weeks age gestational age-optimal) may collect up to 32 weeks
- 4 weeks after post –initiation for oral group or post-completion for intravenous group.
- 8 weeks after treatment post –initiation for oral group or post-completion for intravenous group.
- Delivery\*
- Postpartum day 1\*

\* collected with routine delivery at LPCH. Routine CBC at birth admission and postpartum day 1 with LPCH. This will be in the patient's electronic health record.

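### In early entrants the end of oral treatment falls after the last pill count and survey, and no readable rule covers a 4- or 8-week draw that birth precedes

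*Combined protocol and SAP*

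**What the plan says.** **Treatment length.** Section 6 (after randomization) has oral iron continue until delivery, and the schedule table at the end of section 7.3 gives its window as "24-34 weeks GA up to delivery". IV treatment is one infusion, or two infusions 3-8 days apart.

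**Adherence and symptoms.** Sections 7.1 and 7.2 list oral-arm pill counts at weeks 4 and 8. Section 6 states: "Patients in both groups will complete post-intervention surveys at 1 week, 4 weeks, and 8-12 weeks after initiating therapy". Section 7.2 also gives 8-12 weeks for the last survey, while section 7.6 gives 8 weeks. Under section 7.8, missed doses are reported through the survey. No survey or pill count is listed at delivery. The schedule table continues adverse-event recording through delivery to six weeks postpartum, and section 8 lists a discontinuation item among the data abstracted from the chart.

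**Outcomes that depend on this.** Section 3.2 names the rate of discontinuation and "symptoms of patients before, during, and at the completion of therapy". The synopsis places compliance under the primary safety outcome.

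**Hemoglobin draws.** The table has "Blood draw to check CBC 8 weeks after initiation of oral iron/ post-completion of IV infusions" and a matching 4-week row. Section 6 also counts from completion for the IV arm. Section 7.6 counts from initiation and does not separate the arms.

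**Entry limit.** Section 5.4: "Patients may be included in the study up to 34 weeks 6/7 days". The synopsis: "Between 24-34 weeks' pregnancy". For the randomization labs, section 7.7 has "24-28 weeks (up to 30 complete weeks if necessary" and section 7.9 "may collect up to 32 weeks".

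**The concern.** Follow-up of oral treatment runs on a clock from treatment start, but the treatment ends at delivery. A woman who enters at 24 weeks takes tablets well beyond her last pill count and possibly beyond her last survey. Tablets that she stops late, and symptoms late in treatment, are recorded only if they reach the chart or are reported as an adverse event. The IV course is over within about nine days, so its stopping and its completion fall inside the surveyed period. The likely effect is to understate late stopping in the oral arm alone. Section 2.2 itself cites discontinuation in about half of patients prescribed oral iron, so late stopping is a realistic possibility.

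The same clock creates a second, smaller difficulty at the other end of the entry window. For late entrants a 4- or 8-week draw can fall after birth, and the plan does not say what happens then. If such a draw were taken and analyzed, delivery blood loss and any transfusion would be mixed with the response to iron.

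**Working it through.** The plan gives no figure of its own on this point, and no gestational age at delivery. Delivery timing and the spread of entry are therefore assumptions.

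**Step 1. Early entrants, oral arm.** Treatment weeks = delivery week - entry week. Weeks after the last pill count = treatment weeks - 8. Weeks after a survey at the end of its window = treatment weeks - 12.

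| Entry | Birth | Treatment weeks | After week 8 | After week 12 |
|---|---|---|---|---|
| 24 | 39 | 15 | 7 (47%) | 3 (20%) |
| 24 | 40 | 16 | 8 (50%) | 4 (25%) |
| 28 | 39 | 11 | 3 (27%) | 0 |
| 28 | 40 | 12 | 4 (33%) | 0 |

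Dispensing records would rarely fill the gap. A 100-tablet bottle lasts 200 days at one tablet every other day and 100 days at two. From 24 to 40 weeks is 112 days.

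**Step 2. Late entrants, dates of the draws.** Entry at 34 6/7:
- Oral: 4-week draw at 38 6/7, 8-week draw at 42 6/7.
- Two-infusion IV, counted from completion (add 3-8 days): 39 2/7 to 40 0/7, and 43 2/7 to 44 0/7.
- With birth at 39 0/7, the 8-week draw follows birth for oral entrants after 31 0/7 and for two-infusion IV entrants (8-day gap) after 29 6/7.

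**Step 3. Shares over the whole arm.** Assume entry E is uniform from 24 weeks to a limit L, and delivery B is normal with mean 38.5 or 39 and SD 1.5 or 2 weeks. Let T = B - E. The share of draws after birth is P(T < 4) or P(T < 8). The share of oral treatment weeks after week k is the sum of max(T - k, 0) divided by the sum of T. Simulation with 2 million women per setting gives these ranges over the four delivery settings:

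| Entry limit L | 4-week draw after birth, oral | 8-week draw after birth, oral | Oral weeks after week 8 | Oral weeks after week 12 |
|---|---|---|---|---|
| 34 6/7 | 4.9-8.9% | 35.5-40.1% | 22.6-25.5% | 4.3-6.2% |
| 32 | 0.2-1.3% | 15.3-22.0% | 26.4-29.6% | 5.0-7.3% |
| 30 | 0.0-0.1% | 3.8-9.5% | 30.9-33.9% | 6.1-8.9% |

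Across these limits, 23-34% of oral treatment weeks follow the week-8 pill count and 4-9% follow a week-12 survey. An earlier entry limit shrinks the draw problem and enlarges the adherence gap. A survey done at week 8, as section 7.6 has it, leaves the larger share.

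**Step 4. IV arm.** For two-infusion women with a 5.5-day gap, a clock from completion and entry to 34 6/7, the shares after birth are about 9-14% (4-week) and 43-47% (8-week). One-infusion women have essentially the oral clock. Under section 7.6, which counts from initiation, the extra lag disappears. The proportion of two-infusion women is not given.

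**Step 5. In women.** With 40 per arm (section 4.3) and entry to 34 6/7, 5-9% is 2 to about 4 oral women at week 4, and 36-40% is about 14 to 16 at week 8.

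**The case against.** **A reader might infer that late entrants are in fact drawn postpartum, so that the hemoglobin comparison is contaminated by delivery blood loss.** The documents do not say so and lean the other way. Sections 7.1 and 7.2 arrange the draws around antenatal appointments where that can be done. The table places both columns before delivery, and section 5.6 drops the six-week postpartum study draw. A missing value is at least as likely. The visit-window cells for weeks 4 and 8 and Algorithms B and C cannot be read here, so a rule there cannot be excluded. What stands is that no readable text settles the matter.

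**A reader might infer that the primary analysis is seriously affected.** Section 12.3 takes change over 4 weeks and change pre-delivery as primary, and the delivery-admission CBC serves the second. Week 8, where the large shares lie, is not among the named endpoints. The 4-week share is modest under the widest entry limit and close to nil under the two narrowest.

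**A reader might infer that oral treatment goes unmeasured after weeks 8-12.** That is too strong. Delivery hemoglobin, adverse events, events leading to discontinuation and the discontinuation form are all still recorded. Section 1.1.2 describes follow-up through delivery and postpartum with surveys, and section 7.7 provides a postpartum visit or call. However, neither section schedules a symptom or missed-dose survey at or after delivery. A gap in patient-reported stopping, missed doses and symptoms therefore remains.

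**Burden.** Delivery is documented as chart abstraction, not as a research contact, so a survey there would be a new task. This objection stands, and the fix uses the postpartum contact first.

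**Conclusion.** The point holds as an inexpensive improvement to a stated secondary outcome, together with a clarification of the draw schedule. In early entrants, patient-reported stopping, missed doses and symptoms are cut short in the oral arm only. About 23-34% of oral treatment weeks follow the last pill count, and about 4-9% follow a survey done as late as week 12. For a woman entering at 24 weeks the figures are about half and a fifth to a quarter.

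For the draws, a value preceded by birth would be missing or postpartum, and the readable text does not say which. This concerns about 5-9% of oral 4-week values and 36-40% of 8-week values with entry to 34 6/7 weeks, and about 0-1% and 4-22% with entry stopping at 30-32 weeks. It is somewhat more in two-infusion IV women if their clock starts at completion.

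All shares rest on assumed uniform entry and normal delivery timing (mean 38.5-39, SD 1.5-2 weeks). If 70% of women enter at 24-28 weeks with the limit at 34 6/7, the draw shares fall to 2-4% and 17-20%. The direction of the adherence gap does not depend on these assumptions, but its size does.

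**What to change.** 1. At the existing 6 (4-12) week postpartum visit or call (section 7.7), or during the delivery stay if study staff are present, add a short form covering the period up to delivery. It asks both arms about symptoms. It asks the oral arm for the date of the last tablet, missed doses and, where available, a count of remaining tablets. Add it to the schedule table, and settle whether the last antepartum survey is at week 8 (section 7.6) or weeks 8-12 (sections 6 and 7.2). Cost: one short form and some recall error.
2. State in sections 5.9, 7.1, 7.2 and 7.9 that 4- and 8-week hemoglobin values enter the efficacy analysis only if drawn before delivery. Cost: some values become missing, and their number should be reported by arm.
3. Reconcile the entry and baseline-lab limits (30, 32, 34 and 34 6/7 weeks in the synopsis and sections 5.1, 5.4, 7.7 and 7.9) and the starting point of the IV draw clock (section 7.6 against section 6 and the schedule table). The size of the draw problem depends on both. Cost: wording only.

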# 7.4 Study Procedures by Visit

Research staff trained in obstetric and perinatal outcomes abstraction will be responsible for research data abstraction from patient medical records. Outcomes will be ascertained until delivery and maternal/infant discharge and up to 6 (4-12) weeks postpartum depending on the outcome.

# 7.5 Management of Unscheduled Visits

To facilitate appropriate management of study participants during unscheduled visits, we will:

- Prominently display participant status in the patient's EHR for all providers to see
- Include information regarding the management plan that corresponds to the study group
- Provide the patient with brochure that outlines the study group and management algorithm
- Include contact information to allow study staff to be reached as needed for questions.

